5.5 Prohibited Medications/Treatments

Subjects with pre-existing hypersensitivity to pembrolizumab or other PD-1/PD-L1 pathway inhibitors are disqualified from participation in the trial.

Subjects are prohibited from receiving the following therapies during the Screening and Treatment Phase (including retreatment for post-complete response relapse) of this trial:

- Antineoplastic systemic chemotherapy
- Targeted therapy (e.g. MAPK inhibitors), or biological therapy
- Immunotherapy not specified in this protocol
- Radiation therapy to multiple lesions or major surgery

Note: Radiation therapy or minor surgery to a single pre-existing but currently growing symptomatic extracranial lesion may be considered on an exceptional case-by-case basis after consultation with SYNDAX. The patient must have

measurable disease outside the radiated or operated field. Administration of palliative radiation therapy to a new lesion will be considered clinical progression.

- Live vaccines within 30 days prior to the first dose of trial treatment and while participating in the trial. Examples of live vaccines include, but are not limited to, the following: measles, mumps, rubella, varicella/zoster, yellow fever, rabies, BCG, and typhoid vaccine.
- Systemic glucocorticoids with the exceptions specified in section 4.2.1,
- Any other HDACi, including valproic acid,
- DNA methyltransferase inhibitors,
- Any additional anticancer agents, such as chemotherapy, immunotherapy, targeted therapy, biological response modifiers will not be allowed, even if utilized as treatment of non-cancer indications,
- Any other investigational agents.
- Traditional herbal medicines; these therapies are not fully studied and their use may result in unanticipated drug-drug interactions that may cause or confound the assessment of toxicities.
- Sensitive substrates of CYP1A2, CYP2C8, CYP3A with a narrow therapeutic window (see [APPENDIX A PROHIBITED MEDICATIONS](#)),
- Drugs that are known to inhibit or induce P-gp (see [APPENDIX A PROHIBITED MEDICATIONS](#)).

There are no prohibited therapies during the Post-Treatment and Follow-up Phases.

5.6 Rescue Medications and Supportive Care

Subjects should receive appropriate supportive care measures, as deemed necessary by the treating investigator. Suggested supportive care measures for the management of AEs with potential immunologic etiology are outlined below. Where appropriate, these guidelines include the use of oral or IV treatment with corticosteroids as well as additional anti-inflammatory agents if symptoms do not improve with administration of corticosteroids. Note that several courses of steroid tapering may be necessary as symptoms may worsen when the steroid dose is decreased. For each disorder, attempts should be made to rule out other causes, such as metastatic disease, bacterial or viral infection, which might require additional supportive care. The treatment guidelines will be applied when the investigator determines the events to be related to pembrolizumab.

NOTE: If after the evaluation the event is determined unrelated, the investigator does not need to follow the treatment guidance (as outlined below). Refer to Section 5.3.2 for dose modification guidelines.

It may be necessary to perform conditional procedures, such as bronchoscopy, endoscopy, or skin photography as part of evaluation of the event.

- **Pneumonitis:**

Diagnosis of pneumonitis may require consultation with pulmonology and should not be solely relying on radiographic imaging. If possible, bronchoscopy with bronchoalveolar lavage and/or lung biopsy should be performed.

 - For Grade 2 events, treat with systemic corticosteroids (prednisone 1-2mg/kg daily, or its equivalent). When symptoms improve to Grade 1 or less, steroid taper should be started and continued over no less than 4 weeks.
 - For Grade 3-4 events, immediately treat with intravenous steroids. Administer additional anti-inflammatory measures, as needed.
 - Add prophylactic antibiotics for opportunistic infections in the case of prolonged steroid administration.

- **Diarrhea/Colitis:**

Subjects should be carefully monitored for signs and symptoms of enterocolitis (such as diarrhea, abdominal pain, blood or mucus in stool, with or without fever) and of bowel perforation (such as peritoneal signs and ileus). Given that entinostat may also present with diarrhea, consultation with gastroenterology for possible colonoscopy should be considered. An attribution to specific drug (entinostat or pembrolizumab) should be sought versus a combination of interventions/maneuvers (e.g. entinostat hold and/or rechallenge).

 - All subjects who experience diarrhea/colitis should be advised to drink liberal quantities of clear fluids. If sufficient oral fluid intake is not feasible, fluid and electrolytes should be substituted via IV infusion. For Grade 2 or higher diarrhea, consider GI consultation and endoscopy to confirm or rule out colitis.
 - For Grade 2 diarrhea/colitis attributed to pembrolizumab, administer oral corticosteroids (prednisone 1-2mg/kg daily, or its equivalent).
 - For Grade 3 or 4 diarrhea/colitis attributed to pembrolizumab, treat with intravenous steroids followed by high dose oral steroids.
 - When symptoms attributed to pembrolizumab improve to Grade 1 or less, steroid taper should be started and continued over no less than 4 weeks.
 - For diarrhea associated with entinostat, please consult section 5.3.1.

- **Type 1 diabetes mellitus (T1DM, if new onset, including diabetic ketoacidosis) or ≥ Grade 3 hyperglycemia in patients with pre-existing diabetes, if associated with ketosis (ketonuria) or metabolic acidosis**
 - For T1DM or Grade 3-4 hyperglycemia

- Insulin replacement therapy is recommended for T1DM and for Grade 3-4 hyperglycemia associated with metabolic acidosis or ketonuria.
- Evaluate patients with serum glucose and a metabolic panel, urine ketones, glycosylated hemoglobin, and C-peptide.
- **Hypophysitis:**
 - For Grade 2 events, treat with corticosteroids (prednisone 1-2mg/kg daily, or its equivalent). When symptoms improve to Grade 1 or less, steroid taper should be started and continued over no less than 4 weeks. Replacement of appropriate hormones may be required as the steroid dose is tapered.
 - For Grade 3-4 events, treat with an initial dose of IV corticosteroids followed by oral corticosteroids. When symptoms improve to Grade 1 or less, steroid taper should be started and continued over no less than 4 weeks. Replacement of appropriate hormones may be required as the steroid dose is being tapered.
- **Hyperthyroidism or Hypothyroidism:**

Thyroid disorders can occur at any time during treatment. Monitor patients for changes in thyroid function (at the start of treatment, periodically during treatment, and as indicated based on clinical evaluation) and for clinical signs and symptoms of thyroid disorders.

 - Grade 2 hyperthyroidism events (and Grade 2-4 hypothyroidism):
 - In hyperthyroidism, non-selective β -blockers (e.g. propranolol) are suggested as initial therapy if subject has a resting heart rate >90 beats/min. If free T4 is 30% more than institutional ULN, patient is required to start on anti-thyroid medication (e.g. propylthiouracil, methimazole, tapazole).
 - In hypothyroidism, thyroid hormone replacement therapy, with levothyroxine or liothyronine, is indicated per standard of care.
 - Grade 3-4 hyperthyroidism
 - Treat with an initial dose of IV corticosteroids followed by oral corticosteroids. When symptoms improve to Grade 1 or less, steroid taper should be started and continued over no less than 4 weeks. Replacement of appropriate hormones may be required as the steroid dose is being tapered.

- **Hepatic:**

Given that both entinostat and pembrolizumab can induce transaminitis, a liver biopsy can be considered to exclude autoimmune hepatitis, because management can be vastly different.

- For Grade 1-2 events attributed to pembrolizumab, monitor liver function tests more frequently until returned to baseline values (consider weekly).
 - Treat with IV or oral corticosteroids
- For Grade 3-4 events attributed to pembrolizumab, treat with IV corticosteroids for 24 to 48 hours.
- When symptoms improve to Grade 1 or less, a steroid taper should be started and continued over no less than 4 weeks.
- If transaminitis is attributed to entinostat, please consult section 5.3.1.

- **Renal Failure or Nephritis:**

Although autoimmune interstitial nephritis can occur with pembrolizumab but not entinostat, electrolyte abnormalities due to electrolyte wasting can occur with entinostat. Please consider urinalysis (with urine culture if WBCs in urine are present) and urine electrolytes (Na, Cl, Mg, Phos, Ca²⁺, CO₂) if unexplained low serum electrolytes are observed. Consult nephrology if there is suspicion of autoimmune interstitial nephritis attributed to pembrolizumab.

- For Grade 2 events attributed to pembrolizumab, treat with corticosteroids.
- For Grade 3-4 events attributed to pembrolizumab, treat with systemic corticosteroids.
- When symptoms improve to Grade 1 or less, steroid taper should be started and continued over no less than 4 weeks.

- **Steven-Johnson Syndrome (SJS) and Toxic Epidermal Necrolysis (TEN):**

- For signs or symptoms of SJS or TEN, withhold pembrolizumab and entinostat and refer the patient for specialized care for assessment and treatment.
- If SJS or TEN is confirmed, permanently discontinue pembrolizumab and entinostat.

- **Cardiac Immune-mediated myocarditis:**

Although both entinostat and pembrolizumab can affect heart function, AEs can be different (e.g. entinostat can cause cardiac arrhythmias whereas pembrolizumab can cause myocarditis). Please consult cardiology if any suspicion for cardiac

abnormalities and hold both drugs until cardiology clearance is complete. For suspected immune-mediated myocarditis, ensure adequate evaluation to exclude other etiologies, and administer corticosteroids as appropriate.

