Recurrence of the same hematologic toxicity	If the same hematologic toxicity recurs: 
 1) Administer symptomatic remedies/start prophylaxis. Hold¹ dose until recovery to Grade 1 or baseline. 2) If recovered within 2 weeks, resume study drug as follows: 
 • If receiving 5 mg, restart study drug at 3 mg, • If receiving 3 mg, restart study drug at 2 mg, • If receiving 2 mg, permanently discontinue study drug. 3) If the same \geq Grade 3 event recurs (i.e., third occurrence), despite entinostat dose reduction to 2 mg as described above, permanently discontinue study drug.

If greater than 50% of doses are missed during any 6-week period, discontinue from study drug treatment.

5.3.2 Dose Modification and toxicity management for immune-related AEs associated with pembrolizumab and combination therapy

AE (both non-serious and serious) associated with pembrolizumab exposure, including coadministration with additional compounds, may represent an immunologic etiology. These immune-related AEs (irAEs) may occur shortly after the first dose or several months after the last dose of pembrolizumab/combination treatment and may affect more than one body system simultaneously. Therefore, early recognition and initiation of treatment is critical to reduce complications. Based on existing clinical study data, most irAEs were reversible and could be managed with interruptions of pembrolizumab/combination treatment, administration of corticosteroids and/or other supportive care. For suspected irAEs, ensure adequate evaluation to confirm etiology or exclude other causes. Additional procedures or tests such as bronchoscopy, endoscopy, skin biopsy may be included as part of the evaluation. Dose modification and toxicity management guidelines for irAEs associated with pembrolizumab/combination treatment are provided in the table below. Pembrolizumab must be withheld for drug-related toxicities and severe or life-threatening AEs as per the table provided below. See Section 5.6 for supportive care guidelines, including use of corticosteroids and additional guidance on management of immune-mediated events (i.e., pneumonitis, diarrhea/colitis, Type 1 diabetes mellitus, hypophysitis, hyper/hypothyroidism, hepatotoxicity, renal insufficiency/nephritis, Steven's-Johnson Syndrome, and myocarditis).

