2. Study intervention must be permanently discontinued if the irAE does not resolve or the corticosteroid dose is not ≤ 10 mg/day within 12 weeks of the last study intervention treatment.
3. The corticosteroid taper should begin when the irAE is \leq Grade 1 and continue at least 4 weeks.
4. If study intervention has been withheld, study intervention may resume after the irAE decreased to \leq Grade 1 after corticosteroid taper.

irAEs	Toxicity Grade (CTCAE v5.0)	Action With Pembrolizumab	Corticosteroid and/or Other Therapies	Monitoring and Follow-up
Pneumonitis	Grade 2	Withhold	
 • Administer corticosteroids (initial dose of 1 to 2 mg/kg prednisone or equivalent) followed by taper • Add prophylactic antibiotics for opportunistic infections 	
 • Monitor participants for signs and symptoms of pneumonitis • Evaluate participants with suspected pneumonitis with radiographic imaging and initiate corticosteroid treatment
	Recurrent Grade 2, Grade 3 or 4	Permanently discontinue		

irAEs	Toxicity Grade (CTCAE v5.0)	Action With Pembrolizumab	Corticosteroid and/or Other Therapies	Monitoring and Follow-up
Diarrhea/Colitis	Grade 2 or 3	Withhold	
 Administer corticosteroids (initial dose of 1 to 2 mg/kg prednisone or equivalent) followed by taper 	
 Monitor participants for signs and symptoms of enterocolitis (ie, diarrhea, abdominal pain, blood or mucus in stool with or without fever) and of bowel perforation (ie, peritoneal signs and ileus) Participants with \geqGrade 2 diarrhea suspecting colitis should consider GI consultation and performing endoscopy to rule out colitis Participants with diarrhea/colitis should be advised to drink liberal quantities of clear fluids. If sufficient oral fluid intake is not feasible, fluid and electrolytes should be substituted via IV infusion
	Recurrent Grade 3 or Grade 4	Permanently discontinue		
AST or ALT Elevation or Increased Bilirubin	Grade 2 ^a	Withhold	
 Administer corticosteroids (initial dose of 0.5 to 1 mg/kg prednisone or equivalent) followed by taper 	
 Monitor with liver function tests (consider weekly or more frequently until liver enzyme value returned to baseline or is stable)

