Myocarditis	Grade 1	Withhold	
 Based on severity of AE administer corticosteroids 	
 Ensure adequate evaluation to confirm etiology and/or exclude other causes
	Grade 2, 3 or 4	Permanently discontinue		
Exfoliative Dermatologic Conditions	Suspected SJS, TEN, or DRESS	Withhold	
 Based on severity of AE administer corticosteroids 	
 Ensure adequate evaluation to confirm etiology or exclude other causes
	Confirmed SJS, TEN, or DRESS	Permanently discontinue		
All Other irAEs	Persistent Grade 2	Withhold	
 Based on severity of AE administer corticosteroids 	
 Ensure adequate evaluation to confirm etiology or exclude other causes
	Grade 3	Withhold or discontinue based on the event ^e		
	Recurrent Grade 3 or Grade 4	Permanently discontinue		

AE(s)=adverse event(s); ALT= alanine aminotransferase; AST=aspartate aminotransferase; CTCAE=Common Terminology Criteria for Adverse Events; DRESS=Drug Rash with Eosinophilia and Systemic Symptom; GI=gastrointestinal; IO=immuno-oncology; ir=immune related; IV=intravenous; SJS=Stevens-Johnson Syndrome; T1DM=type 1 diabetes mellitus; TEN=Toxic Epidermal Necrolysis; ULN=upper limit of normal.
 
Note: Non-irAE will be managed as appropriate, following clinical practice recommendations.
				

irAEs	Toxicity Grade (CTCAE v5.0)	Action With Pembrolizumab	Corticosteroid and/or Other Therapies	Monitoring and Follow-up

^a AST/ALT: >3.0 to 5.0 x ULN if baseline normal; >3.0 to 5.0 x baseline, if baseline abnormal; bilirubin: >1.5 to 3.0 x ULN if baseline normal; >1.5 to 3.0 x baseline if baseline abnormal
 
^b AST/ALT: >5.0 to 20.0 x ULN, if baseline normal; >5.0 to 20.0 x baseline, if baseline abnormal; bilirubin: >3.0 to 10.0 x ULN if baseline normal; >3.0 to 10.0 x baseline if baseline abnormal
 
^c AST/ALT: >20.0 x ULN, if baseline normal; >20.0 x baseline, if baseline abnormal; bilirubin: >10.0 x ULN if baseline normal; >10.0 x baseline if baseline abnormal
 
^d The decision to withhold or permanently discontinue pembrolizumab is at the discretion of the investigator or treating physician. If control achieved or ≤ Grade 2, pembrolizumab may be resumed.
 
^e Events that require discontinuation include, but are not limited to: encephalitis and other clinically important irAEs.
				

LCCC 1729
PI: [name].

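### Section 5.6 Hepatic lists corticosteroids for Grade 1-2 liver events attributed to pembrolizumab, but the amended 5.3.2 table starts them, and first withholds pembrolizumab, at Grade 2.

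*Combined protocol and SAP*

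**What the plan says.** Section 5.6, Hepatic, gives this instruction for the lower grades: "For Grade 1-2 events attributed to pembrolizumab, monitor liver function tests more frequently until returned to baseline values (consider weekly"). The sub-bullet beneath it reads "Treat with IV or oral corticosteroids". It states no dose and is not limited to Grade 2. The same list sets the taper: "When symptoms improve to Grade 1 or less, a steroid taper should be started and continued over no less than 4 weeks".

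The table in 5.3.2 has a row for raised AST, ALT or bilirubin whose first entry is Grade 2. There pembrolizumab is withheld and the steroid instruction is "Administer corticosteroids (initial dose of 0.5 to 1 mg/kg prednisone or equivalent) followed by taper". At Grade 3 or 4 pembrolizumab is stopped permanently and the starting dose is 1 to 2 mg/kg. Footnote a defines Grade 2 as "AST/ALT: >3.0 to 5.0 x ULN if baseline normal; >3.0 to 5.0 x baseline, if baseline abnormal", with bilirubin above 1.5 and up to 3.0 times the same references. The row has no Grade 1 entry. General instruction 3 above the table says: "The corticosteroid taper should begin when the irAE is" at Grade 1 or lower.

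The two sections refer to each other. Section 5.3.2 says "See Section 5.6 for supportive care guidelines, including use of corticosteroids and additional guidance on management of immune-mediated events" and names hepatotoxicity among those events. Section 5.6 sends the reader back to 5.3.2 for dose modification and says of its own content: "The treatment guidelines will be applied when the investigator determines the events to be related to pembrolizumab".

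**The concern.** Two parts of the same protocol give different lowest grades for starting steroids in pembrolizumab-related liver toxicity, and neither is said to take precedence. A patient whose AST or ALT rises modestly and is attributed to pembrolizumab could receive systemic steroids under 5.6 that the table does not call for.

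From Grade 2 upward the table pairs liver steroids with withholding or stopping pembrolizumab. At Grade 1 it gives no hold, so a steroid course begun under 5.6 could run alongside continuing infusions. That is avoidable immunosuppression during checkpoint-inhibitor treatment. It could blur response, PFS and the later PBMC samples in the patients concerned.

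The situation can arise in practice. Section 5.3.3 lists AST/ALT elevation as an overlapping toxicity of the two drugs, and section 6.4.2 has liver chemistries checked on day 1 of every cycle.

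**Working it through.** The plan states no figure on this point, so the check is mainly a comparison of text.

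**Liver instructions by grade, events attributed to pembrolizumab**

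| Grade | 5.6 Hepatic | 5.3.2 table |
|---|---|---|
| 1 | Closer liver tests; steroids listed, no dose | No entry: no steroid, no hold |
| 2 | Closer liver tests; steroids listed, no dose | Withhold; 0.5 to 1 mg/kg prednisone or equivalent, then taper |
| 3-4 | IV steroids for 24 to 48 hours | Discontinue permanently; 1 to 2 mg/kg, then taper |

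The lowest grade with steroids is 1 in section 5.6 and 2 in the table. The lowest grade with a pembrolizumab hold in the table is 2.

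**Is the table's silence at Grade 1 an oversight?** Probably not. Where the table wants action at Grade 1 it says so: the myocarditis row withholds pembrolizumab at Grade 1.

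**Does the hepatic line fit the rest of 5.6?** Six headings in 5.6 tie steroids to a grade. Their starting grades are:
- pneumonitis: 2
- diarrhea/colitis: 2
- hypophysitis: 2
- hyperthyroidism: 3
- renal failure/nephritis: 2
- hepatic: 1

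Five of six start at Grade 2 or higher, and hepatic is the exception. Type 1 diabetes and SJS/TEN are not counted because 5.6 gives no steroid instruction for them. Myocarditis is not counted because 5.6 gives no grade for it.

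**Does the taper rule work at Grade 1?** Both sections start the taper once the event is Grade 1 or less. An event that never exceeds Grade 1 meets that condition on the day steroids would begin, so the rule gives no usable starting point for the taper.

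**Would steroids overlap an infusion?** The minimum taper is 4 weeks = 28 days, and pembrolizumab is given every 21 (±2) days, at most 23 days apart on schedule. Since 28 > 23, a course started before the last planned infusion, with no hold, would span at least one infusion.

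**How many patients?** The documents give no rate of Grade 1 liver events attributed to pembrolizumab. The rates below are assumptions that show a range. Expected number = n × p. Chance of at least one = 1 − (1 − p)^n. Here n is 14 (enrolled) or 10 (evaluable), both from section 9.2.

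| Assumed p | Expected, n=14 | At least one, n=14 | Expected, n=10 | At least one, n=10 |
|---|---|---|---|---|
| 5% | 0.7 | 51% | 0.5 | 40% |
| 10% | 1.4 | 77% | 1.0 | 65% |
| 20% | 2.8 | 96% | 2.0 | 89% |

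These count patients who would meet the Grade 1 line. How many would be given steroids depends on the investigator.

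**Primary endpoint.** Section 7.4.2 places the day-22 biopsy before the first pembrolizumab dose, so no event attributed to pembrolizumab can precede it.

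**The case against.** The strongest reply is that 5.6 is advisory. It opens by leaving supportive care to the treating investigator's judgement and calls its measures suggested. The sentence saying the guidelines will be applied is mainly about attribution to pembrolizumab. This stands: no Grade 1 steroid course is mandated.

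A second reply is that the table is silent at Grade 1 rather than contradictory, and that a taper starting on return to Grade 1 implies the steroids were meant for higher grades. A careful clinician might read it that way. The bullet, however, names Grade 1 and places the steroid line under it without qualification. The table cannot correct this, because 5.3.2 points to 5.6 for steroid use.

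Third, the 5.3.2 myocarditis row allows steroids at Grade 1 according to severity, so steroids at that grade are not foreign to this protocol. That is fair, and it weakens the five-of-six pattern somewhat. But that row also withholds pembrolizumab at Grade 1, which nothing does for a Grade 1 liver event.

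Fourth, section 5.5 restricts systemic glucocorticoids, but the exceptions in 4.2.1 do not cover immune-related events at any grade. Read literally, 5.5 would bar the Grade 2 to 4 steroids too. It shows general caution about steroids and does not single out Grade 1.

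Fifth, the affected group may be small. Section 8.1.1 need not count a laboratory change as an adverse event if it requires no entinostat modification, although the note to 4.1.9 leaves room for values that worsen from baseline. Section 5.3.2 says single-drug attribution is difficult. The nearest rates in the protocol are hepatitis at 0.6% (1.5.2) and autoimmune hepatitis at 0.5% (6.2.4). With n = 14 these give 14 × 0.006 = 0.08 and 14 × 0.005 = 0.07 expected cases, about a 7 to 8% chance of any. They describe diagnosed hepatitis rather than Grade 1 enzyme rises, so they do not settle the rate, but they are a reason not to lean on the assumed range.

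**Conclusion.** The concern holds and is minor. As written, 5.6 lists steroids one grade lower than the amended table for pembrolizumab-related liver events. The most likely explanation is a drafting slip: the Amendment 2 summary lists the 5.3.2 table as replaced and does not list 5.6. That is an inference, since the superseded table is not shown.

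The discrepancy is confined to Grade 1. At Grade 2 both sections give steroids, and only the table states a dose. The number of patients affected is unknown; the 0.7 to 2.8 of 14 above rests wholly on assumed rates of 5% to 20%. The primary endpoint is not touched. Any effect on response, PFS or later blood samples would be limited to patients actually given steroids for a Grade 1 event.

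**What to change.** Split the Grade 1-2 bullet in 5.6 Hepatic:

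- **Grade 1 attributed to pembrolizumab:** more frequent liver function tests only, weekly if judged useful.
- **Grade 2 attributed to pembrolizumab:** the same monitoring plus corticosteroids at an initial 0.5 to 1 mg/kg prednisone or equivalent, then taper, as in the 5.3.2 table.

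The clinical team should first confirm that no Grade 1 steroid use was intended. The cost is one reworded bullet in the next amendment, with no new procedures or data.
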